## Abstract

Title	Prostaglandin Inhibition and PD-1/CTLA4 blockade in melanoma
Patient population	Patients with stage III unresectable/ stage IV melanoma
Rationale for Study	Prostaglandin Inhibition may increase the efficacy of immunotherapy
Primary Objective	To evaluate the overall response rate (ORR) by week 12 in patients with stage III unresectable/stage IV melanoma.
Secondary Objectives	To determine the median progression free survival and the overall survival and toxicity profile of this combination.
Study Design	Prospective single arm Simon 2 stage Phase II trial
Number of patients	43
Duration of Follow up	Patients will be followed for 30 days after discontinuation of treatment or removal from study
Duration of study	The study is expected to complete accrual at 24 months.
Study Drugs	Aspirin Pembrolizumab Ipilimumab
Safety Assessments	CTCAE v. 4 will be used to assess toxicity.
Efficacy Assessments	RECIST version 1.1 will be used in this study for assessment of tumor response.
Unique Aspects of this Study	Combination trial with ipilimumab, pembrolizumab, and aspirin.

## List of Abbreviations

AE	adverse event
ALP	alkaline phosphatase
ALT	alanine aminotransferase
ANC	absolute neutrophil count
AST	aspartate aminotransferase
ATC	Anatomical Therapeutic Chemical (Classification System)
AUC	area under the curve
BUN	blood urea nitrogen
CBC	complete blood cell (count)
CHR	Committee on Human Research (UCSF IRB)
CR	complete response
CRC	Clinical Research Coordinator
CRF	case report form
CSF	cerebral spinal fluid
CT	computerized tomography
CTCEA	Common Terminology Criteria for Adverse Events
CTEP	Cancer Therapy Evaluation Program
CTMS	Clinical Trial Management System
DFS	disease-free survival
DLT	dose limiting toxicity
DSMC	Data and Safety Monitoring Committee
DSMP	Data and Safety Monitoring Plan
ECOG	Eastern Cooperative Oncology Group

## 1 Introduction

### 1.1 Background on Indication

The combination of ipilimumab and nivolumab is considered one of the standard treatments for advanced melanoma(1). However, even with this treatment, 40% of patients do not have an objective response. Recently, it has been shown in a preclinical model that the addition of a cyclooxygenase (COX) inhibitor may reduce PD-1 resistance(2, 3) In the study by Zelenay et al, aspirin, which blocks both COX-1 and COX-2, was able to prevent PD-1 resistance in a melanoma model. While the initial ipilimumab nivolumab study used nivolumab as the PD-1 inhibitor, these results have been recently replicated with pembrolizumab, a very similar anti-PD-1 inhibitor (Long G, et al ASCO 2016).

### 1.2 Background on the Immunotherapy Combinations

#### 1.2.1 Pembrolizumab

Pembrolizumab is a potent and highly selective humanized monoclonal antibody (mAb) of the IgG4/kappa isotype designed to directly block the interaction between PD-1 and its ligands, PD-L1 and PD-L2. KeytrudaTM (pembrolizumab) has recently been approved in the United States for the treatment of patients with unresectable or metastatic melanoma and disease progression following ipilimumab and, if BRAF V600 mutation positive, a BRAF inhibitor(4-7).

The importance of intact immune surveillance in controlling outgrowth of neoplastic transformation has been known for decades. Accumulating evidence shows a correlation between tumor-infiltrating lymphocytes (TILs) in cancer tissue and favorable prognosis in various malignancies. In particular, the presence of CD8+ T-cells and the ratio of CD8+ effector T-cells / FoxP3+ regulatory T-cells seems to correlate with improved prognosis and long-term survival in many solid tumors(8).

The PD-1 receptor-ligand interaction is a major pathway hijacked by tumors to suppress immune control(5). The normal function of PD-1, expressed on the cell surface of activated T-cells under healthy conditions, is to down-modulate unwanted or excessive immune responses, including autoimmune reactions. PD-1 (encoded by the gene Pdcd1) is an Ig superfamily member related to CD28 and CTLA-4 which has been shown to negatively regulate antigen receptor signaling upon engagement of its ligands (PD-L1 and/or PD-L2). The structure of murine PD-1 has been resolved. PD-1 and family members are type I transmembrane glycoproteins containing an Ig Variable-type (V-type) domain responsible for ligand binding and a cytoplasmic tail which is responsible for the binding of signaling molecules. The cytoplasmic tail of PD-1 contains 2 tyrosine-based signaling motifs, an immunoreceptor tyrosine-based inhibition motif (ITIM) and an immunoreceptor tyrosine-based switch motif (ITSM). Following T-cell stimulation, PD-1 recruits the tyrosine phosphatases SHP-1 and SHP-2 to the ITSM motif within its cytoplasmic tail, leading to the dephosphorylation of effector molecules such as CD3ζ, PKCθ and ZAP70 which are involved in the CD3 T-cell signaling cascade. The mechanism by which PD-1 down modulates T-cell responses is similar to, but distinct from that of CTLA-4 as both molecules regulate an overlapping set of signaling proteins. PD-1 was shown to be expressed on activated lymphocytes including peripheral CD4+ and CD8+ T-cells, B-cells, Tregs and Natural Killer cells. Expression has also been shown during thymic development on CD4-CD8- (double negative) T-cells as well as subsets of macrophages and dendritic cells. The ligands for PD-1 (PD-L1 and PD-L2) are constitutively expressed or can be induced in a variety of cell types, including non-hematopoietic tissues as well as in various tumors. Both ligands are type I transmembrane receptors containing both IgV- and IgC-like domains in the extracellular region and contain short cytoplasmic regions with no known signaling motifs. Binding of either PD-1 ligand to PD-1 inhibits T-cell activation triggered through the T-cell receptor. PD-L1 is expressed at low levels on various non-

hematopoietic tissues, most notably on vascular endothelium, whereas PD-L2 protein is only detectably expressed on antigen-presenting cells found in lymphoid tissue or chronic inflammatory environments. PD-L2 is thought to control immune T-cell activation in lymphoid organs, whereas PD-L1 serves to dampen unwarranted T-cell function in peripheral tissues. Although healthy organs express little (if any) PD-L1, a variety of cancers were demonstrated to express abundant levels of this T-cell inhibitor. PD-1 has been suggested to regulate tumor-specific T-cell expansion in subjects with melanoma (MEL). This suggests that the PD-1/PD-L1 pathway plays a critical role in tumor immune evasion and should be considered as an attractive target for therapeutic intervention.

### 1.2.2 Ipilimumab

Successful stimulation of T cells by antigen presenting cells require both antigen presentation by the MHC molecule-antigen peptide complex to the T cell receptor as well as costimulation by the B7 molecule on the antigen presenting cells to the CD 80/86 molecule. Ipilimumab is a humanized monoclonal antibody to CTLA-4 which is a decoy receptor. The effect of ipilimumab binding to CTLA-4 is to increase costimulation and increase T cell activation.

The two currently approved immune checkpoint blockers are anti-CTLA-4 and anti-PD-1 antibodies. The first, anti-CTLA4 antibody, ipilimumab was evaluated for treatment of advanced melanoma in two phase III trials as a monotherapy, and in combination with dacarbazine(9)(10). In these studies, ipilimumab demonstrated an increase overall response rate (ORR), median progression free survival (PFS), and median overall survival (OS) compared to a gp100 vaccine or in combination with dacarbazine vs. dacarbazine alone. Ipilimumab both at the tested 3mg/kg dose and at the 10 mg/kg dose was associated with increased immune related toxicities such as colitis, diarrhea, dermatitis, as well as a characteristic immune related hypophysitis(11).

Following the successful development of ipilimumab in melanoma, the development of anti-PD1 agents proceeded rapidly following the FDA approval of ipilimumab for advanced melanoma. In initial phase I clinical trials, two anti-PD-1 agents, pembrolizumab and nivolumab exhibited favorable response rates between 20-40% with substantial decreased frequency for grade 3-4 adverse events (10-15%)(12-13). Subsequent phase III trials showed durable clinical benefit with improved ORR, OFS, and OS from both pembrolizumab and nivolumab administered as first line therapies when compared to ipilimumab (KEYNOTE-006(14), CheckMate 067 trials(15), respectively).

With the anti-tumor benefit of both anti-CTLA4 and anti-PD1 agents administered as monotherapies, the logical next step was the administration of both immunotherapies in combination. Phase II data of ipilimumab and nivolumab in combination followed by nivolumab maintenance exhibited an increased toxicity profile compared to agents administered as monotherapies (50% of patients with grade 3-4 adverse events)(16). Yet despite the heightened toxicity profile, the clinical benefit seen in the combination was promising with improved ORR and PFS when compared to either ipilimumab or nivolumab alone (CheckMate 067)(15). Thus, while the clinical benefit has been promising, an increased propensity to develop grade 3/4 adverse events remains a strong consideration in choosing the proper context to administer the combination of nivolumab and ipilimumab.

The dose of ipilimumab does not appear to play a role in response rate but the dose does appear to play a role in side effects and adverse events. A recent trial, the Keynote 029 trial showed that the combination of pembrolizumab at the 200 mg dose and ipilimumab 1 mg/kg X 4 was associated with a reduced incidence of grade 3/4 AE to ~ 20% and an ORR of 55%(17). This reduced ipilimumab dose appears to be a well tolerated and equi-efficacious dose compared to

the higher dose ipilimumab regimens. For combination therapies, this is considered to be a good regimen.

### 1.2.3 Aspirin

Aspirin, in the form of leaves from the willow tree, has been used for its health effects for at least 2,400 years. In 1853, chemist Charles Frédéric Gerhardt synthesized acetyl salicylic acid in the lab for the first time. In 1897, scientists at Bayer began studying acetylsalicylic acid as a less-irritating replacement for common salicylate medicines. In 1899, Bayer had named the drug Aspirin(18).

In 1971, British pharmacologist John Robert Vane, showed aspirin suppressed the production of prostaglandins and thromboxanes. Aspirin's ability to suppress the production of prostaglandins and thromboxanes is due to its irreversible inactivation of the cyclooxygenase enzyme required for prostaglandin and thromboxane synthesis. Aspirin acts as an acetylating agent where an acetyl group is covalently attached to a serine residue in the active site of the PTGS enzyme.

Low-dose aspirin use irreversibly blocks the formation of thromboxane A2 in platelets, producing an inhibitory effect on platelet aggregation during the lifetime of the affected platelet (8–9 days). This antithrombotic property makes aspirin useful for reducing the incidence of heart attacks in people who have had a heart attack, unstable angina, ischemic stroke or transient ischemic attack 40 mg of aspirin a day is able to inhibit a large proportion of maximum thromboxane A2 release provoked acutely, with the prostaglandin I2 synthesis being little affected; however, higher doses of aspirin are required to attain further inhibition.

#### COX-1 and COX-2 inhibition

At least two different types of cyclooxygenases, COX-1 and COX-2, are acted on by aspirin. Aspirin irreversibly inhibits COX-1 and modifies the enzymatic activity of COX-2. COX-2 normally produces prostanoids, most of which are proinflammatory. Aspirin-modified PTGS2 (prostaglandin synthetase 2) produces lipoxins, most of which are anti-inflammatory

However, several of the new COX-2 inhibitors, such as rofecoxib (Vioxx), have been withdrawn in the last decade, after evidence emerged that PTGS2 inhibitors increase the risk of heart attack and stroke. Endothelial cells lining the microvasculature in the body are proposed to express PTGS2, and, by selectively inhibiting PTGS2, prostaglandin production (specifically, PGI2; prostacyclin) is downregulated with respect to thromboxane levels, as PTGS1 in platelets is unaffected. Thus, the protective anticoagulative effect of PGI2 is removed, increasing the risk of thrombus and associated heart attacks and other circulatory problems. Since platelets have no DNA, they are unable to synthesize new PTGS once aspirin has irreversibly inhibited the enzyme, an important difference with reversible inhibitors.

Furthermore, aspirin, while inhibiting the ability of COX-2 to form pro-inflammatory products such as the prostaglandins, converts this enzyme's activity from a prostaglandin-forming cyclooxygenase to a lipoxygenase-like enzyme: aspirin-treated COX-2 metabolizes a variety of polyunsaturated fatty acids to hydroperoxy products which are then further metabolized to specialized proresolving mediators such as the aspirin-triggered lipoxins, aspirin-triggered resolvins, and aspirin-triggered maresins. These mediators possess potent anti-inflammatory activity. It is proposed that this aspirin-triggered transition of COX-2 from cyclooxygenase to lipoxygenase activity and the consequential formation of specialized proresolving mediators contributes to the anti-inflammatory effects of aspirin.

Recently, COX-2 inhibition has been proposed as a mechanism for reducing MDSC activity in some models of cancer and thereby assisting PD-1 effectiveness(3). In these preclinical models,

COX blockade synergizes with PD-1 inhibition in melanoma, colorectal cancer and in other syngeneic immunocompetent models. Furthermore the same COX signature was seen in cutaneous melanoma(3). The calculated human dose extrapolated from animal models is 1 gm twice daily.

### 1.3 Rationale for the Proposed Study

PD-1 inhibition is associated with dramatic and long lasting responses in melanoma. However, 40-60 % of patients do not respond to anti-PD-1 or anti-PD-L1 blocking antibodies. Recent reports of PD-1+CTLA4 blocking combinations have shown increased response rates. The combination of ipilimumab and nivolumab has demonstrated response rates in the ~60% range (19). The combination of low dose ipilimumab and standard dose pembrolizumab has been explored in a recent clinical trial and shown an ORR of 55%. However, there remains a residual 40% of patients where this combination is still not effective.

Our analysis has shown that many PD-1 non-responders share certain characteristics such as elevated LDH, liver metastasis, as well as increased tumor burden and non-cutaneous origin (21-23). Collectively, many of these melanoma patients have low fractions of partially exhausted cytotoxic T lymphocytes (peCTL). For these “low peCTL” tumors, ipilimumab + PD-1 combination therapy with ipilimumab and PD-1 inhibitors is the current standard of care. We hypothesize that the addition of aspirin to this modified ipilimumab pembrolizumab regimen will increase response rates.

Recent reports have highlighted other pathways that may be involved (20) such as iNOS, COX-2 activation, Myeloid Derived Suppressor Cells and Treg activation. A recent report provides powerful support for the COX-2 pathway as an escape mechanism(3). These authors showed that ablation of the COX-2 pathway or PGE synthetase in mice with the BRAFV600E mutation or the NRAS G12D mutation shifts cells towards the classic PD-1 escape pathway and hence sensitizes them to anti-PD-1 antibodies. The dose of aspirin was extrapolated from these mouse experiments.

### 1.4 Rationale for Dose Selection/Regimen/Modification

An open-label Phase I trial (Protocol 001) is being conducted to evaluate the safety and clinical activity of single agent MK-3475. The dose escalation portion of this trial evaluated three dose levels, 1 mg/kg, 3 mg/kg, and 10 mg/kg, administered every 2 weeks (Q2W) in subjects with advanced solid tumors. All three dose levels were well tolerated and no dose-limiting toxicities were observed. This first in human study of MK-3475 showed evidence of target engagement and objective evidence of tumor size reduction at all dose levels (1 mg/kg, 3 mg/kg and 10 mg/kg Q2W). No MTD has been identified to date. 10.0 mg/kg Q2W, the highest dose tested in PN001, will be the dose and schedule utilized in Cohorts A, B, C and D of this protocol to test for initial tumor activity. Recent data from other clinical studies within the MK-3475 program has shown that a lower dose of MK-3475 and a less frequent schedule may be sufficient for target engagement and clinical activity.

PK data analysis of MK-3475 administered Q2W and Q3W showed slow systemic clearance, limited volume of distribution, and a long half-life (refer to IB). Pharmacodynamic data (IL-2 release assay) suggested that peripheral target engagement is durable (>21 days). This early PK and pharmacodynamic data provides scientific rationale for testing a Q2W and Q3W dosing schedule.

A population pharmacokinetic analysis has been performed using serum concentration time data from 476 patients. Within the resulting population PK model, clearance and volume parameters of MK-3475 were found to be dependent on body weight. The relationship between clearance and

body weight, with an allometric exponent of 0.59, is within the range observed for other antibodies and would support both body weight normalized dosing or a fixed dose across all body weights. MK-3475 has been found to have a wide therapeutic range based on the melanoma indication. The differences in exposure for a 200 mg fixed dose regimen relative to a 2 mg/kg Q3W body weight based regimen are anticipated to remain well within the established exposure margins of 0.5 – 5.0 for MK-3475 in the melanoma indication. The exposure margins are based on the notion of similar efficacy and safety in melanoma at 10 mg/kg Q3W vs. the proposed dose regimen of 2 mg/kg Q3W (i.e. 5-fold higher dose and exposure). The population PK evaluation revealed that there was no significant impact of tumor burden on exposure. In addition, exposure was similar between the NSCLC and melanoma indications. Therefore, there are no anticipated changes in exposure between different indication settings.

The rationale for further exploration of 2 mg/kg and comparable doses of pembrolizumab in solid tumors is based on: 1) similar efficacy and safety of pembrolizumab when dosed at either 2 mg/kg or 10 mg/kg Q3W in melanoma patients, 2) the flat exposure-response relationships of pembrolizumab for both efficacy and safety in the dose ranges of 2 mg/kg Q3W to 10 mg/kg Q3W, 3) the lack of effect of tumor burden or indication on distribution behavior of pembrolizumab (as assessed by the population PK model) and 4) the assumption that the dynamics of pembrolizumab target engagement will not vary meaningfully with tumor type.

The choice of the 200 mg Q3W as an appropriate dose for the switch to fixed dosing is based on simulations performed using the population PK model of pembrolizumab showing that the fixed dose of 200 mg every 3 weeks will provide exposures that 1) are optimally consistent with those obtained with the 2 mg/kg dose every 3 weeks, 2) will maintain individual patient exposures in the exposure range established in melanoma as associated with maximal efficacy response and 3) will maintain individual patients exposure in the exposure range established in melanoma that are well tolerated and safe.

A fixed dose regimen will simplify the dosing regimen to be more convenient for physicians and to reduce potential for dosing errors. A fixed dosing scheme will also reduce complexity in the logistical chain at treatment facilities and reduce wastage.

The combination of ipilimumab and pembrolizumab is considered one of the most effective regimens currently in use (Long et al, ASCO 2016) with an ORR of >50% with reduced grade 3/4 toxicities compared to the combination of ipilimumab and nivolumab. Given that this current combination is adding a drug (ASA), ipilimumab pembrolizumab is a better choice for the baseline regimen

The addition of ASA is based on preclinical data showing the effectiveness of ASA in increasing responses to anti-PD-1 antibodies(3)In this study mice were administered aspirin orally at 600  $\mu$ g/mL. translating this dose to a human dose, approximately 1,800-2,400 mg/day would be appropriate. In a twice daily dose this would be 975 mg (total 1,950 mg/day).

## 1.5 Correlative Studies

We have recently described the CD8+ CTLA-4 high/PD-1 high fraction in the tumor as being directly proportional to the response rate. We plan to determine the proportion of patients with this marker <20% who have a response as this will be representative of patients who we would not expect to have a response with monotherapy PD-1 alone(21).

## 2 Objectives of the Study

### 2.1 Primary

To evaluate the overall response rate (ORR) by week 12 in patients with stage III unresectable/stage IV melanoma

### 2.2 Secondary

To determine the median progression free survival, overall survival, and toxicity profile of the combination of ipilimumab, pembrolizumab and high dose aspirin in patients with stage III unresectable/IV melanoma.

### 2.3 Endpoints

#### 2.3.1 Primary Endpoints

- Objective Response Rate (ORR)

#### 2.3.2 Secondary Endpoints

- Toxicity, according to CTCAE v. 4
- Profession Free Survival (PFS)
- Overall Survival (OS)

## 3 Study Design

### 3.1 Characteristics

This is a single arm, single institution, open label, prospective, Phase II clinical trial with a Simon stage II design with an early stopping rule. In the first stage 11 patients will be accrued. If  $\leq 7$  responses are seen here then the trial will be stopped for futility. If  $>7$  responses are seen then the trial will be continued and a full 43 patients will be enrolled.

Patients will take aspirin daily and receive combination therapy with pembrolizumab and ipilimumab every 3 weeks for 4 cycles. After 4 cycles, ipilimumab will be discontinued and patients will receive pembrolizumab every 3 weeks and continue taking aspirin daily.

### 3.2 Number of Subjects

A total of 43 subjects will be enrolled.

### 3.3 Eligibility Criteria

Patients must have baseline evaluations performed prior to the first dose of study drug and must meet all inclusion and exclusion criteria. In addition, the patient must be thoroughly informed about all aspects of the study, including the study visit schedule and required evaluations and all regulatory requirements for informed consent. The written informed consent must be obtained from the patient prior to enrollment. The following criteria apply to all patients enrolled onto the study unless otherwise specified.

### 3.3.1 Inclusion Criteria

1. Patients must have histologically confirmed melanoma that is metastatic or unresectable and for which standard curative or palliative measures do not exist or are no longer effective
2. Age >18 years
3. Eastern Cooperative Oncology Group (ECOG) performance status of 0 to 1.
4. Requirements for organ and marrow function:

Adequate bone marrow function:

leukocytes	≥ 3,000/mcL
absolute neutrophil count	≥ 1,500/mcL
platelets	≥ 100,000/mcL

Adequate hepatic function:

total bilirubin	within normal institutional limits
total bilirubin	≤ 1.5 X institutional upper limit
AST(SGOT)	≤ 2.5 X institutional upper limit of normal
ALT(SGPT)	≤ 2.5 X institutional upper limit of normal

Adequate renal function:

creatinine	≤ 1.5 X ULN
------------	-------------

5. Women of childbearing potential should have a negative urine or serum pregnancy within 72 hours prior to receiving the first dose of study drug. If the urine test is positive or cannot be confirmed as negative, a serum pregnancy test will be required.
6. Women of childbearing potential (Section 5.6.2) must be willing to use an adequate method of contraception, as outlined in Section 5.6.2 – Contraception, for the course of the study through 120 days after the last dose of study medication.

Note: Abstinence is acceptable if this is the usual lifestyle and preferred contraception for the subject.

7. Men of childbearing potential (Section 5.6.2) must agree to use an adequate method of contraception as outlined in Section 5.6.2- Contraception, starting with the first dose of study therapy through 120 days after the last dose of study therapy.

Note: Abstinence is acceptable if this is the usual lifestyle and preferred contraception for the subject.

8. Ability to understand a written informed consent document, and the willingness to sign it.

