## 8 Statistical Analysis Plan

### 8.1 Statistical Analysis Plan Summary

This is a non-randomized prospective Phase II clinical trial with a Simon stage II design with an early stopping provision. The primary objective is to evaluate the overall response rate (ORR) by week 12 in patients with stage III unresectable/stage IV melanoma. The hypothesis is that the study treatment regimen will have a clinical meaningful improvement in ORR by week 12. H0 is for an ORR by week 12 = 60% while Ha is for an ORR by week 12= 80%. 60% is used as a threshold for the H0 based on published data (19).

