### 8.2 Sample Size and Accrual Rate Considerations

#### 8.2.1 Sample Size and Power Estimate

A two-stage Simon's optimal design is used for the study to test the null hypothesis that the ORR by week 12 is 60% or less versus the alternative hypothesis that the ORR by week 12 is greater than 80% using an one-sided test with 5% level of significance with the power of 80% for alternative hypothesis. An initial 11 evaluable patients will be accrued at the end of stage 1. If at least 4 or more overall responders (CR/PR per RECIST 1.1) from stage 1 are observed, the study will continue to enroll additional 32 evaluable patients in the stage 2. The null hypothesis will be rejected at the 5% level of significance (one-sided) if there are 30 or fewer ORR by week 12 among all 43 evaluable patients by the end of stage 2. If the ORR rate is 60%, the probability of ending the study during the first stage is 70%; if the ORR rate is indeed 80%, the probability of study will be terminated at the first stage is 16%. The significance level of the study is 0.05 and the power is 0.80 for the study design.

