### 8.3 Interim Analyses and Stopping Rules

The two stage sequential design of this study has a decision timepoint based on the counts of CR or PR (per RECIST 1.1) from stage 1 by at least 4 months post-initial treatment regimen of the 11 patients with measurable disease at baseline, to either stop or initiate stage 2 of the study. In the first stage 11 patients will be accrued. If  $\leq 7$  responses are seen here then the trial will be stopped

for futility. If >7 responses are seen then the trial will be continued an a full 43 patients will be enrolled.

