## 8.4 Statistical Analysis Plan

This is a Simon 2 stage Phase II prospective clinical trial. The statistical plan will be for an optimal 2 stage design with the  $P_0=0.6$  and  $P_1=0.8$ . If <30 responses are seen then the experimental hypothesis has been rejected. The type 1 error is 0.0489 and the power is 0.8024. The probability of early stopping if the response rate is  $P_0=20.5\%$

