### 8.4.1 Analysis of Primary Endpoints

The primary efficacy endpoint of the study is the objective response rate (ORR), which is defined as the proportion of subjects for whom the best overall response by week 12 at the time of data cutoff is confirmed CR or PR as per RECIST. RECIST version 1.1 will be used in this study for assessment of tumor response. While either CT or MRI may be utilized, as per RECIST 1.1, CT is the preferred imaging technique in this study. In the primary analysis, point estimates of ORR and 95% confidence intervals will be provided. Subjects who do not have any post-baseline tumor assessments will be considered as non-responders. Supportive analysis of ORR may be performed to include response based on investigator assessment. If sufficient responses are observed, additional supportive analyses may be conducted in subgroups defined by baseline characteristics.

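### Measurable disease is assumed at the interim but not required at entry, and 'evaluable' is undefined, so patients who cannot reach a RECIST partial response may be enrolled and counted

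*Combined protocol and SAP*

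**What the plan says.** - **Eligibility.** Section 3.3.1, item 1: "Patients must have histologically confirmed melanoma that is metastatic or unresectable". None of the 8 inclusion items or the 10 exclusion items in section 3.3.2 mentions measurable disease.
- **Interim.** Section 8.3 counts stage-1 responses in "the 11 patients with measurable disease at baseline". Section 3.1 gives the same stopping rule but speaks only of 11 patients.
- **Endpoint.** Section 8.4.1 defines ORR as confirmed CR or PR by week 12 and adds: "RECIST version 1.1 will be used in this study for assessment of tumor response".
- **Denominator.** Sections 8.2.1 and 8.2.3 plan for 43 *evaluable* patients without defining the word. Section 8.2.3 allows up to 50 enrolled to cover drop-outs and non-evaluable patients. Section 3.2 sets total enrolment at 43.
- **Missing responses.** Section 8.4.1 counts patients with no post-baseline scan as non-responders. Section 8.2.2 does the same for patients of unknown response who stop because of adverse events. Neither rule covers a patient who is scanned on schedule but had no measurable lesion at baseline.
- **Screening scan.** Appendix 1 schedules tumor imaging at screening, with no lesion criterion attached.

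**The concern.** Partial response is defined by shrinkage of measured target lesions. On the standard reading of RECIST 1.1, which the protocol names but does not reprint, a patient with only non-measurable disease can reach CR but not PR. Section 8.3 appears to rely on such patients being absent, yet nothing at entry keeps them out.

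If one enrols, the plan does not say whether that patient counts. Counting the patient pulls the observed ORR below the rate in patients for whom the endpoint works as intended, in a design that needs 8 responses in 11 to continue and 31 in 43 to succeed. Leaving the patient out relies on an undefined term and uses up part of the enrolment margin. In an open-label single-arm trial, that choice should be fixed before any response is seen.

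**Working it through.** **Inputs.** Null ORR 60% and alternative 80% (section 8.1); one-sided 5% level and 80% power (section 8.2.1). Stage 1 has 11 patients and continues on more than 7 responses (sections 3.1 and 8.3). The total is 43, with a final cutoff of 30, read as rejecting the null at 31 or more. Section 8.2.1 words the interim and final rules differently (at least 4 responders to continue; rejection "if there are 30 or fewer ORR by week 12 among all 43 evaluable patients by the end of stage 2"), but only 7/11 and 30/43 reproduce the plan's error rates.

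**Formula.** With response probability p1 in stage 1 and p2 in stage 2,

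P(reject) = Σ (x = 8 to 11) P(X = x) × P(Y ≥ 31 − x), where X ~ Bin(11, p1) and Y ~ Bin(32, p2).

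**Reproducing the plan.** At p1 = p2 = 0.80 the four terms are:

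- x = 8: 0.2215 × 0.9102 = 0.2016
- x = 9: 0.2953 × 0.9589 = 0.2831
- x = 10: 0.2362 × 0.9833 = 0.2323
- x = 11: 0.0859 × 0.9939 = 0.0854

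The sum is 0.8024. At 0.60 the same formula gives 0.0489. Section 8.4 says "The type 1 error is 0.0489 and the power is 0.8024", so both agree. P(X ≤ 7) is 0.704 at 60% and 0.161 at 80%, matching the 70% and 16% in section 8.2.1.

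**Adding patients without measurable disease.** Let q be their share among counted patients and c their response rate (CR only). The effective rate is p(1 − q) + cq. For example, q = 5% and c = 0 gives 0.80 × 0.95 = 0.76; q = 10% gives 0.80 × 0.90 = 0.72. The documents give neither q nor c, so all values below are assumptions.

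| q | Power, both stages, c = 0 | Power, stage 2 only, c = 0 | Power, both stages, c = 20% |
|---|---|---|---|
| 0 | 0.802 | 0.802 | 0.802 |
| 2% | 0.744 | 0.781 | 0.759 |
| 5% | 0.639 | 0.737 | 0.685 |
| 10% | 0.442 | 0.626 | 0.542 |

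The stage-2-only column keeps p1 = 0.80 and lowers p2 alone. It corresponds to following section 8.3's restriction at the interim and counting everyone afterwards.

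**Error direction.** With both stages affected and c = 0, type I error (60% in measurable patients) falls from 0.0489 to 0.036, 0.021 and 0.008 at q = 2%, 5% and 10%. The chance of stopping at stage 1 when the measurable-disease ORR is 80% rises from 0.161 to 0.198, 0.260 and 0.372.

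**One such patient among the first 11.** If that patient is counted and does not respond, the other 10 must supply 8 responses. P(X ≤ 7) for Bin(10, 0.80) is 0.322, against 0.161. This requires section 8.3's restriction not to be applied.

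**If *evaluable* requires measurable disease.** q is 0 among counted patients and power stays at 0.802. The cost falls on the margin of 50 − 43 = 7 patients (7/50 = 14%). With 5% to 10% of 50 lacking measurable disease, 2.5 to 5 of those 7 places are used, leaving 2 to 4.5 for drop-outs and every other reason.

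**The case against.** The strongest reply is that the statistical section already contains the restriction. Section 8.3 names patients with measurable disease, and sections 8.2.1 and 8.2.3 count *evaluable* patients with an allowance for non-evaluable ones. Read together, they would keep patients without measurable disease out of both the 11 and the 43, with no power lost. That reading is reasonable, but it is not secured: *evaluable* is undefined, section 3.2 counts enrolled patients, and no rule removes these patients from the primary analysis.

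Five stronger readings are tempting, and the documents do not support them:

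- *Power is 0.639 or 0.442.* These figures need an assumed share, no CRs at all in such patients, and dilution of stage 1 despite section 8.3. They are the unfavorable edge of the scenarios for those shares.
- *One patient doubles the false futility risk from 16% to 32%.* This is true only if section 8.3's restriction is not followed.
- *Patients with all lesions resected are clearly eligible.* Item 1 requires disease that is metastatic or unresectable, so a patient with none remaining is a doubtful fit.
- *Leaving such patients out biases the result.* Measurability can be fixed from the pre-treatment scan. Bias arises only if the decision is taken once response is known.
- *The gap favors a positive result.* Dilution lowers type I error as well as power.

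**Conclusion.** The gap is real. The interim rule presupposes measurable disease and the endpoint depends on it, but eligibility does not require it and the analysis denominator is not defined tightly enough to make up for that.

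Its size is conditional. For assumed shares of 2% to 10%, power lies between 0.442 and 0.802, depending on the share, on the CR rate in such patients, on whether stage 1 is restricted as section 8.3 says, and on what *evaluable* means. The documents settle none of these except, by its wording, the stage-1 restriction. With that restriction followed and no responses among these patients in stage 2, power is 0.781, 0.737 or 0.626. The consequence is a missed effect or, if stage 1 is diluted, a false futility stop. The conclusion also rests on the standard RECIST 1.1 reading that PR needs measurable lesions.

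**What to change.** 1. Add to section 3.3.1: at least one measurable lesion by RECIST 1.1 on the screening scan.
2. Define *evaluable* in section 8.2.1 to include that requirement, judged on the screening scan before treatment starts.
3. Use that one population in sections 8.2.1, 8.3 and 8.4.1, and make section 3.2 say whether 43 is the number enrolled or the number evaluable.
4. State in section 8.4.1 how a patient found after enrolment to have had no measurable lesion at baseline is handled, so that the choice cannot depend on outcome.

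The cost is small: the screening scan is already in Appendix 1, and no treatment or visit changes. A few candidates without measurable disease would not be enrolled, so the result would not speak for them. With the requirement in place, the design keeps its stated power of 0.8024 and type I error of 0.0489 on this point.
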